11.5.3 Pharmacokinetic / pharmacodynamic interactions

The relationship between LMB763 PK parameters (Cmax and AUCtau) and key PD parameters (including, but not limited to FGF19, C4, ALP, Cholesterol (total LDL and HDL)) may be explored using a graphical approach and descriptive statistics may be provided. Additional statistical analysis such as ANOVA or regression may be performed, if necessary. Modeling approach may also be used to explore the PK/PD interactions.

11.5.4 Other assessments

Change from baseline itch VAS measurements will be analyzed using the same repeated measures ANCOVA described in [Section 11.4.2](#).

Corporate Confidential Information

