2.2 Secondary objectives

Secondary objectives	Endpoints related to secondary objectives

 To evaluate the pharmacokinetics (PK) of LMB763 in NASH patients. 	
 PK blood collection and analysis (C_{max}, T_{max}, AUC, R_{acc}, etc.).

 To determine the effect of LMB763 on intrahepatic lipid after 12 weeks of treatment. 	
 Percent (%) Liver fat as measured by Magnetic Resonance Imaging (MRI).

 To determine the effect of LMB763 on anthropometric assessments after 12 weeks of treatment. 	
 Weight, BMI, waist-to-hip (WTH) ratio.

 To determine the effect of LMB763 on non-invasive markers of liver fibrosis. 	
 Fibroscan[®] (in a subset of patients) Fibrosis biomarker test (originally known as Fibrotest[®]/FibroSure[®]).

 To determine the effect of LMB763 on fasting lipid profile. 	
 Fasting lipid profile.

 To determine the effect of LMB763 compared with placebo with respect to occurrence and impact of potential itch. 	
 Itch scored on 100 mm visual analog scale (VAS) ratings.

3 Investigational plan

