8.5.6 Clinical Outcome Assessments (COAs)

Visual Analog Scale (VAS)

10 cm visual analogue scale (VAS) will be used to assess the severity of patients itch (ranging from 0 = no itch at all to 10 = the worst imaginable itch). The score (distance from left) on the VAS will be recorded by the patient marking with a line and used to test for an effect of LMB763 over placebo.

The scale will be completed by patients as indicated in [Section 8.1 \(Assessment schedule\)](#).

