9.1 Adverse events

An adverse event (AE) is any untoward medical occurrence (i.e., any unfavorable and unintended sign [including abnormal laboratory findings], symptom or disease) in a patient or clinical investigation patient *after providing written informed consent* for participation in the study until the end of study visit. Therefore, an AE may or may not be temporally or causally associated with the use of a medicinal (investigational) product.

In addition, all reports of intentional misuse and abuse of the study treatment are also considered an adverse event irrespective if a clinical event has occurred. See [Section 9.5](#) for an overview of the reporting requirements.

The occurrence of adverse events must be sought by non-directive questioning of the patient at each visit during the study. Adverse events also may be detected when they are volunteered by the patient during or between visits or through physical examination finding, laboratory test finding, or other assessments.

Abnormal laboratory values or test results constitute adverse events only if they fulfill at least one of the following criteria:

- they induce clinical signs or symptoms,
- they are considered clinically significant,
- they require therapy.

Clinically significant abnormal laboratory values or test results should be identified through a review of values outside of normal ranges/clinically notable ranges, significant changes from baseline or the previous visit, or values which are considered to be non-typical in patients with underlying disease. Investigators have the responsibility for managing the safety of individual patient and identifying adverse events. Alert ranges for liver and kidney related events are included in [Section 9.3](#) and [Section 9.4](#), respectively.

Adverse events must be recorded on the Adverse Events CRF under the signs, symptoms or diagnosis associated with them, and accompanied by the following information:

1. the Common Toxicity Criteria (CTC) AE grade (version 4.0 or higher) for the adverse event. If CTC-AE grading does not exist for an adverse event, use:
 - 1 = mild,
 - 2 = moderate,
 - 3 = severe
 - 4 = life threatening* (see [Section 9.2](#) for definition of a serious adverse event (SAE))
*Note: There may be cases where a CTCAE with a grade of 4 (life-threatening) may not necessarily be an SAE (e.g. certain laboratory abnormalities in the absence of meeting other seriousness criteria).

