 - Number and percentage of subjects with adverse events by system organ class
- Pharmacokinetic (PK) results for plasma:
 - Arithmetic mean (SD) concentration-time plot per treatment (overlying).
 - Summary statistics for PK parameters.
- Pharmacodynamic (PD) analyses include, but are not limited to:
 - Treatment response at Week 12 in ALT
 - Mean (SE) ALT plot per treatment (overlying) over time
 - Treatment comparison of key secondary parameters (Percent liver fat as measured by MRI, Weight, Fibroscan[®], ELF panel, fasting lipid profile and itch as assessed on the VAS scale) at Week 12

- Mean (SE) plots of key secondary parameters (Percent liver fat as measured by MRI, Weight, Fibroscan[®], ELF panel, fasting lipid profile and itch as assessed on the VAS scale) per treatment (overlying) and over time.

Corporate Confidential Information

4 Statistical methods: Analysis sets

For all analysis sets, subjects will be analyzed according to the study treatment(s) received. All placebo subjects will be pooled. Subjects with dose frequency/dose change due to AE will be analyzed according to the treatment they received up to the dose frequency/dose change.

All patients that received at least one dose of study drug will be included in the safety data analysis “safety population”.

The PK analysis set will include all subjects with at least one available valid (i.e., not flagged for exclusion) PK concentration measurement, who received any study drug and experienced no protocol deviations with relevant impact on PK data.

All patients with evaluable PD parameter data and no major protocol deviations impacting PD data will be included in the PD data analysis “PD population”.

For the End of Study (EOS) visit only data from study completers will be included in the summary/analysis tables/figures.

The data exclusion for each analysis set based on protocol deviation codes will be captured in the following table, which will be completed in a SAP amendment prior to DBL as needed.

Table 4-1 Protocol deviation codes and analysis sets

Category Deviation code	Text description of deviation	Data exclusion
	Subjects are excluded from all (safety) analysis in case of these protocol deviations:	Exclude subject completely from all (safety) analysis sets
	Subjects are excluded from PK analysis in case of these protocol deviations:	Exclude subject from PK analysis set

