6.2.3 Statistical model, assumptions and hypotheses

Log-transformed ratio to baseline % liver fat and fasting lipid profiles as well as change from baseline % liver fat, weight, BMI, WTH ratio and itch VAS score will be analyzed. Parameters with more than one post-treatment measurement will be subjected to the same repeated measures ANCOVA described for the primary analysis using log-transformed baseline in lieu of untransformed baseline as a covariate for the log-transformed data analysis. For parameters with only one post-treatment measurement an ANCOVA with treatment as a classification factor and baseline (or log-transformed baseline if applicable) as a covariate will be employed.

Fibroscan® (in a subset of patients), ELF and fibrosis biomarker test data will be analyzed similarly and the log-transformation applied prior to the analysis as needed. For % liver fat, if historical placebo control data in a similar patient population are identified in the literature or become available from in-house studies later on then they may be incorporated into a Bayesian analysis as described for ALT.

The subgroup of subjects with baseline liver fat $\geq 10\%$ may be analyzed separately as needed.

Corporate Confidential Information

7 Statistical methods for safety and tolerability data

All subjects within the Safety analysis set will be included in the safety data analysis.

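### The itch objective is occurrence and impact versus placebo, but the only model-based comparison is of mean VAS change; add a per-patient occurrence and maximum-change comparison

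*Protocol*

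**What the plan says.** **Objective.** Protocol 2.2 (repeated in the synopsis and SAP 1.3.2): "To determine the effect of LMB763 compared with placebo with respect to occurrence and impact of potential itch".

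**Endpoint.** The one endpoint listed against it is "Itch scored on 100 mm visual analog scale (VAS) ratings". Protocol 8.5.6 describes the instrument as a severity scale: "10 cm visual analogue scale (VAS) will be used to assess the severity of patients itch".

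**Model.** Protocol 11.5.4: "Change from baseline itch VAS measurements will be analyzed using the same repeated measures ANCOVA" that Protocol 11.4.2 sets out for ALT. SAP 6.2.3 says the same for change from baseline: "weight, BMI, WTH ratio and itch VAS score will be analyzed". That model includes treatment, visit and their interaction, and is tested one-sided at 0.05.

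**First interpretable results.** In SAP section 2, the list of key secondary parameters to be compared between treatments ends "fasting lipid profile and itch as assessed on the VAS scale) at Week 12". The same section plans mean (SE) plots of these parameters by treatment over time.

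**Descriptive summaries.** SAP 6.2.2 plans listings by subject and visit, and means, SDs, medians, minima and maxima by treatment and visit.

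**Adverse events.** Protocol 9.1 says that adverse events "must be sought by non-directive questioning of the patient at each visit". Protocol 11.4.4 and SAP 7.2 tabulate numbers and percentages by preferred term and treatment. SAP 7.2 adds tables by toxicity grade and by relationship to study drug.

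**Pooling.** SAP section 4 pools all placebo patients.

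**The concern.** Occurrence is a property of a patient: did this person develop itch at any time on treatment? A mean VAS change at one visit is a different quantity. It averages those who itch over those who do not, and it leaves out anyone whose itch has gone by that visit.

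Itch can ease before Week 12 for ordinary reasons. Protocol 6.6 lets tolerability problems be met by interruption or dose adjustment, and some patients stop treatment. Episodes that fall at different visits in different patients are thinned out at each one.

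Protocol 3.7 says pruritus will be closely monitored because it was seen with a bile acid derived FXR agonist. The same sentence says it has not been noted with LMB763. This is the first study in patients, so the question is open. The trial gives patients a direct itch scale but does not use it to count who itched. It names impact as part of the question, and no visible instrument measures it.

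**Working it through.** **1. Objective against analysis.**

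| Part of the objective | Where it is addressed |
|---|---|
| Occurrence, versus placebo | Pruritus AE table by arm and grade (descriptive); no VAS-based count |
| Impact, versus placebo | Nothing visible |
| Severity (what the VAS measures) | Repeated measures ANCOVA on mean change; summaries and plots by visit |

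Text is blacked out after Protocol 11.5.4 and after SAP 6.2.3, so nothing is concluded about it.

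**2. The plan's own figures.** No power is stated for itch. The ALT figures in Protocol 11.7 confirm the set-up (one-sided 0.05, SD 41.16, difference 19 U/L), using power = Φ(δ / [σ√(1/n₁+1/n₂)] − 1.645):

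- 54 v 54: 41.16 × √(2/54) = 7.92; 19/7.92 = 2.40; Φ(0.75) = 77% (stated 76%).
- 54 v 27: 41.16 × √(1/54+1/27) = 9.70; 19/9.70 = 1.96; Φ(0.31) = 62% (stated 61%).

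Both agree to within 2 points. With 27 placebo completers per cohort pooled as in SAP section 4, each dose is compared with 27 + 27 = 54.

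**3. How averaging and resolution act (assumed rates).** The documents give no itch rate or VAS distribution. Assume itch in 25% on LMB763 and 5% on placebo, a rise of mean m = 45 mm and SD s = 15 mm, and zero change in everyone else. If a share r has resolved by Week 12, the proportion itching then is q = (1−r)p. The mean difference is (1−r) × 0.20 × 45, and the variance in each arm is q(m²+s²) − q²m². For 54 v 54:

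| Resolved by Week 12 | Mean difference | Variances, LMB763 / placebo | SE | Power |
|---|---|---|---|---|
| 0 | 9.0 mm | 435.9 / 107.4 | √(543.3/54) = 3.17 | Φ(2.84−1.645) = 88% |
| 50% | 4.5 mm | 249.6 / 55.0 | √(304.6/54) = 2.375 | Φ(1.895−1.645) = 60% |
| 80% | 1.8 mm | 107.4 / 22.3 | √(129.7/54) = 1.55 | Φ(1.16−1.645) = 31% |

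The difference in occurrence stays at 20 percentage points in every row. For a comparison of proportions, p̄ = 0.15, the null SE is √(0.15 × 0.85 × 2/54) = 0.0687 and the alternative SE is √((0.1875+0.0475)/54) = 0.0660. Power is Φ((0.20 − 1.645 × 0.0687)/0.0660) = Φ(1.32) = 91%.

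**4. Simulation.** Several thousand trials per scenario, with the same rates. Further assumptions: 80% of patients have a baseline VAS of 0, there are four post-baseline visits, and an occurrence is a rise of at least 20 mm.

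| Power for 0 / 50 / 80% resolved | 54 v 54 | 54 v 27 |
|---|---|---|
| ANCOVA at Week 12 | 88 / 61 / 27% | 72 / 39 / 7% |
| Maximum change, ANCOVA | about 89% throughout | about 72% throughout |
| Any rise ≥20 mm, Fisher | about 86% | about 62–67% |
| Any rise ≥20 mm, z-test | about 91% | about 78–81% |

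With 5% in both arms, the z-test rejects about 6% of the time at 54 v 54 and Fisher about 1%. At 54 v 27 both are at most 3%. The expected placebo events are only 0.05 × 54 = 2.7 and 0.05 × 27 = 1.35, so a small-sample method is needed.

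**5. Earlier visits.** If every patient peaks at the same visit, the planned model's contrast at that visit recovers about 89% power at 54 v 54, even when itch later resolves. If onsets are scattered over the visits, the contrast at the first post-baseline visit has about 44%.

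**6. A second pattern.** Take 20% v 5% at 54 v 54, with itchers at 40 mm (SD 20). If itch persists, the mean comparison has 72%, a chi-square on any itch 79% and Fisher 71%. If itchers itch at about half of four visits, the Week 12 mean has 46%, or 28% with 10 mm of scoring noise. Any itch at any visit has 78–79%.

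**The case against.** The case on the other side has real force.

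- **The planned model is not a Week 12 test alone.** It gives a treatment contrast at each visit, and mean plots over time are planned. This stands. Itch that peaks early and together would be seen. Scattered onsets would not be recovered in the same way.
- **Occurrence is partly covered.** Pruritus is counted by arm and grade from questioning at every visit. A reader might infer that only spontaneous reports are counted, or that no comparison of itch frequency is possible; Protocol 9.1 and SAP 7.2 do not support that. The table is descriptive, however, and non-directive questioning does not ask each patient about itch as the VAS does.
- **Placebo is pooled.** The 7% and 39% figures belong to 54 v 27. They should not be read as the power of the main comparison, which is about 54 v 54.
- **The gain depends on the test and the pattern.** If itch persists, an exact test is no better than the mean comparison, and the highest proportion figures come from a z-test with very few placebo events.
- **The rates are invented.** So are the VAS distribution, the resolution rates and the 20 mm cut-off. The itch VAS row is also not legible in the schedule as supplied, so the number of VAS visits is assumed.
- **The trial calls itself non-confirmatory.** Itch is one of several secondary variables. This limits the weight of the point but does not remove the mismatch with the objective.

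**Conclusion.** A cheap improvement. The text alone establishes that the objective names occurrence and impact, that the only model-based comparison is of mean VAS change, and that no visible analysis counts who itched on the VAS or measures impact. The gap is partial because of the AE tables and the earlier-visit contrasts.

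The size is conditional. Under 25% v 5% with a peak of about 45 mm and pooled placebo, Week 12 power runs from about 88% (itch persists) through 61% (half resolves) to 27% (80% resolves). A per-patient comparison has about 85–91%. At 54 v 27 the figures are about 72/39/7% against 62–81%. If itch persists to Week 12 there is little or no gain, and most of the missed signal then comes from sample size.

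A reader might infer that the trial would declare no itch difference while several times more patients itch on LMB763, or that pruritus is an established effect of this drug. The documents support neither: the AE table, plots and other visits would also be on view, and Protocol 3.7 says pruritus has not been noted with LMB763.

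**What to change.** In SAP 6.2.3, add for each LMB763 dose versus pooled placebo:

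1. Each patient's maximum post-baseline VAS change, analysed by a baseline-adjusted ANCOVA with the same covariates. This needs no cut-off.
2. The proportion of patients with any post-baseline VAS increase at or above a pre-set cut-off, with risk difference and 90% CI by a small-sample (exact or score) method.

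Keep the repeated measures model and report all three beside the pruritus AE table. State the cut-off in one unit, since the documents describe the scale both as 100 mm and as 0 to 10. Either name a measure of impact or reword the objective to occurrence and severity.

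The cost is a few lines of SAP text and one table from data already collected. The main downside is the cut-off. The sponsor team is unblinded throughout (Protocol 3.1 and 6.4), so the cut-off must be fixed and documented before that team reviews itch by arm. A maximum also picks up scoring noise in both arms, so the cut-off should sit clearly above it.

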11.7 Sample size calculation

A mean decrease of 11 U/L from baseline to Week 12 in ALT was observed in the placebo group (N=142) of the FLINT trial. Historical placebo control data from trials such as the FLINT study will be used when analyzing ALT data from the current study by including prior information in a Bayesian approach.

Data from 54 patients in an LMB763 dosing arm and 54 placebo patients (placebo data from the current study supplemented by historical placebo control data), will provide approximately

76% power to detect a 19 U/L placebo-adjusted reduction from baseline ALT. The sample size calculation was done using a one-sided test at the 0.05 significance level, assuming a standard deviation of 41.16 U/L which was derived from the FLINT trial. A placebo-adjusted 19 U/L reduction in ALT corresponds to a 30 U/L decrease if the mean reduction induced by the placebo treatment is 11 U/L as reported in the FLINT study.

The corresponding power without using any historical placebo control data will be 61% if 54 patients in a LMB763 dosing arm and 27 patients in the placebo arm complete the study.

To make allowance for potential dropouts approximately 96 patients will be enrolled in the each dosing cohort. All patients who have been enrolled into the initial cohort will complete the protocol at that dose, however no further patients will be recruited into that cohort

Corporate Confidential Information

11.8 Power for analysis of key secondary variables

Data from a total of 81 patients (54 from an LMB763 dosing arm and 27 placebo patients) will provide 52% and 82% power to detect a 1.64% and 2.46% difference in absolute change from baseline % liver fat between the 2 treatments, respectively, based on a one-sided test at the 0.05 significance level. It is assumed the standard deviation equals to 4.02%, derived from the summary results in a recently completed Novartis study that enrolled non-alcoholic fatty liver disease patients with baseline liver fat >10% as measured by MRI. Since the observed overall mean baseline % liver fat in that study is 16.39%, a placebo-adjusted absolute decrease of 1.64% and 2.46% corresponds to a relative reduction of 10% and 15%, respectively.

Corporate Confidential Information

12 Ethical considerations

12.1 Regulatory and ethical compliance

This clinical study was designed and shall be implemented, executed and reported in accordance with the ICH Harmonized Tripartite Guidelines for Good Clinical Practice, with applicable local regulations (including European Directive 2001/20/EC, US Code of Federal Regulations Title 21, and Japanese Ministry of Health, Labor, and Welfare), and with the ethical principles laid down in the Declaration of Helsinki.

12.2 Responsibilities of the investigator and IRB/IEC

Before initiating a trial, the investigator/institution must obtain approval/favorable opinion from the Institutional Review Board/Independent Ethics Committee (IRB/IEC) for the trial protocol, written informed consent form, consent form updates, patient recruitment procedures (e.g. advertisements) and any other written information to be provided to patients. Prior to study start, the investigator is required to sign a protocol signature page confirming his/her agreement to conduct the study in accordance with these documents and all of the instructions and procedures found in this protocol and to give access to all relevant data and records to Novartis monitors, auditors, Novartis Quality Assurance representatives, designated agents of Novartis, IRBs/IECs, and regulatory authorities as required. If an inspection of the clinical site is requested by a regulatory authority, the investigator must inform Novartis immediately that this request has been made.

For multi-center trials, a Coordinating Investigator will be selected by Novartis around the time of Last Patient Last Visit to be a reviewer and signatory for the clinical study report.

12.3 Publication of study protocol and results

The key design elements of this protocol will be posted in a publicly accessible database such as clinicaltrials.gov. In addition, upon study completion and finalization of the study report the results of this trial will be either submitted for publication and/or posted in a publicly accessible database of clinical trial results.

13 Protocol adherence

This protocol defines the study objectives, the study procedures and the data to be collected on study participants. Additional assessments required to ensure safety of patients should be administered as deemed necessary on a case by case basis. Under no circumstances is an

investigator allowed to collect additional data or conduct any additional procedures for any research related purpose involving any investigational drugs under the protocol.

Investigators ascertain they will apply due diligence to avoid protocol deviations. If an investigator feels a protocol deviation would improve the conduct of the study this must be considered a protocol amendment, and unless such an amendment is agreed upon by Novartis and approved by the IRB/IEC and health authorities, where required, it cannot be implemented.

Optimization of nutrition-related practices can result in a marked triglyceride-lowering effect that ranges between 20% and 50%. These practices include weight loss, reducing simple carbohydrates at the expense of increasing dietary fiber, eliminating industrial-produced trans fatty acids, restricting fructose and saturated fatty acids, implementing a Mediterranean-style diet, and consuming marine-derived omega-3 PUFA.

AHA recommends the following:

Eat a variety of fruit and vegetable servings every day. Dark green, deep orange, or yellow fruits and vegetables are especially nutritious. Examples include spinach, carrots, peaches, and berries. Eat a variety of grain products every day. Include whole-grain foods that have lots of fiber and nutrients. Examples of whole grains include oats, whole wheat bread, and brown rice. Eat fish at least 2 times each week. Oily fish, which contain omega-3 fatty acids, are best for your heart. These fish include tuna, salmon, mackerel, lake trout, herring, and sardines. Stay at a healthy weight by balancing the amount of calories you eat with the activity you do every day. If you want to lose weight, increase your activity level to burn more calories than you eat.

Eat foods low in saturated fat and cholesterol. Try to choose the following foods:

- Lean meats and meat alternatives like beans or tofu
- Fish, vegetables, beans, and nuts
- Nonfat and low-fat dairy products
- Polyunsaturated or monounsaturated fats, like canola and olive oils, to replace saturated fats, such as butter

Read food labels and limit the amount of trans fat you eat. Trans fat is found in many processed foods made with shortening or with partially hydrogenated or hydrogenated vegetable oils. These foods include cookies, crackers, chips, and many snack foods.

Limit sodium intake to less than 2,300 mg of sodium a day (about one teaspoon). Choose and prepare foods with little or no salt.

Limit alcohol intake to 2 drinks a day for men and 1 drink a day for women.

Limit drinks and foods with added sugar.
